7.0 Calendar of Tests and Procedures

Calendar of Tests and Procedures									
Test	Base line ⁶	C1D1 ⁷	C1D2	C2 D1	C2D2	C3D1	C3D2	3-4 Month Followup ^{8, 11}	6-9 Month Followup
Physical Exam	X	X		X		X		X	X
Medical history/treatment history	X	X							
Vital signs ¹	X	X	X	X	X	X	X	X	X
Medication list	X	X		X		X		X	X
GFR if indicated ²	X	X		X		X		X ¹²	X
Blood Tests ³	X	X	X ¹⁴	X	X ¹⁴	X	X ¹⁴	X	X
QOL questionnaire	X	X						X ¹³	
Pregnancy Test ⁴	X	X ⁹	X ⁹	X	X ⁹	X	X ⁹		
⁶⁸ Ga-DOTATOC (TATE) PET/CT	X								X
Diagnostic CT or MRI	X							X	X
⁹⁰ Y-DOTATOC Therapy (& Amino Acids)			X		X		X		
Skin assessment ¹⁵			X		X		X		
Dosimetry (blood & imaging)			X		X		X		
Adverse Event Assessment	X ⁵	X	X	X		X		X	X
Fluid diary ¹¹		X	X	X	X	X	X		

1. temp, pulse, respirs, b/p, weight. Height at baseline only. Weight at baseline and Day 1 of each cycle.

2. required for children(<18 years). Required for adults (18 and older) if serum creatinine >1.2mg/dl. If required at baseline for patient, then all subsequent time points require nuclear GFR also.

3. blood tests include: CBC/diff, AST, ALT, creatinine, plus urinalysis at baseline only and T.Bili at baseline only.

4. required for females of child bearing potential only

5. Documentation of baseline symptoms

6. All baseline evaluations within 30 days of first ⁹⁰Y-DOTATOC dose except blood tests need to be within 10 days and ⁶⁸Ga-DOTATOC/TATE PET/CT needs to be within 6 months of first ⁹⁰Y-DOTATOC infusion. The diagnostic scans need to be within 120 days of the first ⁹⁰Y-DOTATOC infusion.

7. events only repeated prior to treatment 1 if they fall outside of the baseline windows noted in footnote 6.

8. Patients who discontinue dosing of ⁹⁰Y-DOTATOC early and who have received at least 1 dose of ⁹⁰Y-DOTATOC are also required to complete follow up appointments per calendar

9. repeat testing can be point of care urine pregnancy test done in Nuclear Medicine.
10. Patients will be instructed to have fluid intake of 1.5 liters Day 1 and 2 liters/day on Days 3 & 4.
11. 3-4 month follow up procedures may be performed by patient's local MD.
12. If GFR is indicated, patients will be required to return to UIHC.
13. If patient does not return to UIHC for F/U, QOL may be mailed or e-mailed to patient.
14. Electrolytes will be drawn during the last hour of amino acid infusion.
15. The skin at the site of the infusion will be assessed by clinic visit or phone at 3-5 days following each infusion of amino acids.

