5.0 Eligibility Criteria

5.1 Inclusion Criteria

1. Disease not amenable to standard treatment (nonresectable or disease present after one or more surgeries and/or Sandostatin treatment) or subject has failed existing first line chemotherapy, biologic therapy, targeted agent therapy or radiation therapy.
2. Participation in Iowa Neuroendocrine Tumor Registry.

3. A pathologically confirmed (histology or cytology) malignant neoplasm with at least one target lesion that is confirmed by conventional imaging and is determined to express somatostatin receptors by ⁶⁸Ga-DOTATOC (TATE) PET within 6 months prior to treatment with ⁹⁰Y-DOTATOC.
4. The target lesion is one that either has never received external beam radiation or has been previously irradiated and has since demonstrated progression. Any local irradiation of the target lesion or any non-target lesions via external beam, conformal or stereotactic radiation treatments must have occurred more than 4 weeks prior to study drug administration. Any full cranial-spinal radiation, whether or not a target lesion is included in the field, must have occurred more than 3 months prior to study drug administration.
5. Life expectancy \geq 2 months at the time of study drug administration.
6. Archival tissue from a previous biopsy will be required.
7. Age \geq 6 months-90 years at the time of study drug administration.
8. Performance status as determined by Karnofsky \geq 60 or Lansky Play Scale \geq 60% at the time of study drug administration.
9. Completion of Norfolk Quality of Life Questionnaire.
10. Within 7-10 days of study drug administration, patients must have normal organ and marrow function as defined below:
 - absolute neutrophil count \geq 1000/mm³
 - Platelets \geq 90,000/mm³
 - total bilirubin <3X ULN for age
 - AST(SGOT) & ALT(SGPT) \leq 10X institutional upper limit of normal for age
 - Urinalysis no greater than 1+ hematuria or proteinuria
Adults(age18 or >): Serum creatinine \leq 1.2 mg/dl; if serum creatinine is >1.2 mg/dL, nuclear GFR will be measured.
GFR will need to be \geq 80 ml/min/1.73m² for subjects \leq 40 years old,
 - Renal function* \geq 70 ml/min/1.73m² for subjects between 41-50;
 \geq 60 ml/min/1.73m² for subjects between 51-60;
 \geq 50 ml/min/1.73m² for subjects > 60 years old.

Children(age <18): nuclear GFR \geq 80 mL/min/1.73 m²
- * Renal function criteria based on our previous experience with ⁹⁰Y-DOTATOC therapy and known changes in GFR with age^{13,21,33-35}

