6.0 Imaging and Treatment Plan

**Phase II,
Dosimetry-Guided, Peptide Receptor Radiotherapy (PRRT) with
⁹⁰Y-DOTA-tyr³-Octreotide (⁹⁰Y-DOTATOC) in Children and Adults
with Neuroendocrine and other Somatostatin Receptor Expressing Tumors**

Treatment Cycles and Followup		Imaging and Treatment Schedule	Initial ⁹⁰ Y-DOTATOC Dose	Cumulative ⁹⁰ Y-DOTATOC Dose	Cumulative Renal Radiation
Cycle 1 Week 1	Day 1	Physical exam with height, weight, vitals, labs, list, GFR, pregnancy test; QOL questionnaire Start 18 hrs IV/PO fluids			
	Day 2	⁹⁰ Y-DOTATOC + IV amino acids Continue IV/PO fluids for 48 hrs	50 mCi/m ² in children; 120 mCi in adults	120 mCi maximum	
	Day 4	⁹⁰ Y-DOTATOC PET/CT			
Cycle 2 Week 7-9	Day 1	Physical exam with height, weight, vitals, labs, med list, GFR, pregnancy test Start 18 hrs IV/PO fluids			
	Day 2	⁹⁰ Y-DOTATOC + IV amino acids Continue IV/PO fluids for 48 hrs	Dosimetry determined	270 mCi maximum	
	Day 4	⁹⁰ Y-DOTATOC PET/CT			
Cycle 3 Week 13-17	Day 1	Physical exam with height, weight, vitals, labs, list, GFR, pregnancy test Start 18 hrs IV/PO fluids			
	Days 2-3	⁹⁰ Y-DOTATOC + IV amino acids Continue IV/PO fluids for 48 hrs	Dosimetry determined	420 mCi maximum	≤ 23 Gy
FU	3 months after treatment 3	Physical exam with height, weight, vitals, labs, med list, GFR; QOL questionnaire, diagnostic CT (MRI)			
	6-9 months after treatment 3	Physical exam with height, weight, vitals, labs, med list, GFR; diagnostic CT (MRI) ⁶⁸ Ga-DOTATOC PET/CT;			

Treatment consists of 3 cycles, 6-8 weeks apart. Cycle 1 dose is fixed. Cycles 2 and 3 doses will be determined by dosimetry-based calculation of renal doses from previous cycles; total renal dose ≤ 23Gy.

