$$1000 \times (23 \text{ Gy} - \text{summed renal dose (Gy)}) / \text{renal dose per activity (mGy/MBq)}.$$

All subjects will receive a concomitant amino acid infusion as renal protectant¹³. A parenteral amino acid solution which supplies ≥ 27 g each of lysine and arginine in 2 liters of normal saline (≤ 800 mOsm/L) will be administered IV at a max of 8.3 mL/kg/hour (max 450 mL/hr) for 4 hours to begin 30 minutes prior to infusion of ⁹⁰Y-DOTATOC. Initial infusion rate should be 300mL/hr or less; if tolerated for initial 30 min, rate may be increased to max rate. The total minimum volume which shall be infused is 1600 mL. This will constitute an off-label use of these approved amino acid solutions due to the higher than recommended volume infused. Any further information regarding dosing should be obtained from the manufacturer's instructions.

Patients will be pre-medicated with EMEND and Lorazepam, and/or another anti-emetic, 30 minutes prior to the Amino Acid infusion.

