13.3 Previous Human Experience with ⁹⁰Y-DOTATOC

⁹⁰Y-DOTATOC PRRT was also pioneered in Europe where it has been demonstrated to be the most effective therapy to date for patients with neuroendocrine tumors, with a mean time to disease progression is greater than 4 years^{23,38}. University of Iowa investigators participated in an international Phase II study of ⁹⁰Y-DOTATOC PRRT and enrolled over 40 subjects. This clinical trial also demonstrated safety and efficacy of PRRT in humans when care is taken to protect the kidneys with concomitant amino acid infusion²¹. University of Iowa investigators also hold the only IND (#61,907) in the United States for this radiopharmaceutical and have completed the only Phase I trial of ⁹⁰Y-DOTATOC PRRT in children. University of Iowa investigators have treated 18 children and young adults as well as 40 older adults with ⁹⁰Y-DOTATOC PRRT; no irreversible renal toxicity has been experienced in these patients, primarily due to rigorous hydration prior to and after administration of the therapy as well as providing the total dose in 3 moderately sized doses rather than 2 higher doses. The major goal of this present study will be to determine if individualized, dosimetry-guided dosing of ⁹⁰Y-DOTATOC can successfully optimize dose to tumor while limiting renal toxicity for every patient.

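### Calendar footnote 10 prints one adult-sized fluid intake for every patient, although children from 6 months of age are eligible

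*Combined protocol and SAP*

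**What the plan says.** Section 7.0, footnote 10, tells staff: "Patients will be instructed to have fluid intake of 1.5 liters Day 1 and 2 liters/day on Days 3" and 4. The subject of the sentence is patients in general, and nothing in it depends on age or size.

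Section 5.1 item 7 sets the eligible age as "6 months-90 years at the time of study drug administration", with 6 months as the lower bound.

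The treatment schedules (the opening schema and section 6.0) also ask for fluids, for example "Start 18 hrs IV/PO fluids" on Day 1 and a further 48 hours after dosing. They give durations and an IV or oral route, but no volume.

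Elsewhere the protocol does separate children from adults. Cycle 1 activity in section 6.0 is 50 mCi/m² "in children; 120 mCi in adults". Calendar footnote 2 has its own GFR rule for those under 18, and section 10.1 asks for an ACE inhibitor dose suited to age.

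**The concern.** Read literally, footnote 10 gives a 6-month-old the same daily volume as a full-grown adult. For the smallest eligible subjects that is the wrong instruction.

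Hydration is also a protective part of this treatment. Section 1.4 names the kidney as the normal organ at greatest risk. Section 13.3 says that no irreversible renal toxicity occurred in the group's earlier patients, "primarily due to rigorous hydration prior to and after administration of the therapy" (together with giving the total in three moderate doses). A child's volume should therefore be the right one for that child. Simply exempting children from the footnote would leave it without a paediatric volume.

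The calendar would not readily expose a problem. Electrolytes are drawn in the last hour of the amino acid infusion (footnote 14) and are not in the routine blood tests of footnote 3. No electrolyte check is listed for Days 3 and 4, when the larger oral volume applies.

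**Working it through.** **Inputs from the protocol.** 1.5 L on Day 1 and 2 L/day on Days 3 and 4 (section 7.0, footnote 10); minimum age 6 months (section 5.1 item 7); Cycle 1 activity 50 mCi/m² in children and 120 mCi in adults (section 6.0).

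**Assumptions, not in the documents.** Weight and height: 6.5 kg and 65 cm, or 10 kg and 76 cm, for the smallest children; 20 kg and 115 cm for an older child; 70 kg and 170 cm for an adult.

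**Step 1: volume per kg.** Formula: mL ÷ kg.

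| Weight | Day 1 (1500 mL) | Days 3 and 4 (2000 mL) |
|---|---|---|
| 6.5 kg | 231 mL/kg | 308 mL/kg |
| 10 kg | 150 mL/kg | 200 mL/kg |
| 20 kg | 75 mL/kg | 100 mL/kg |
| 70 kg | 21 mL/kg | 29 mL/kg |

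Relative to the 70 kg adult, the per-kg volume is 70/10 = 7 times as large at 10 kg and 70/6.5 = 10.8 times as large at 6.5 kg. Taking 1 L as about 1 kg, 2 L/day is 2/10 = 20% to 2/6.5 = 31% of body weight in these children.

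**Step 2: the same volume per m².** Surface area = √(kg × cm / 3600).

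- 6.5 kg: √(6.5 × 65 / 3600) = 0.343 m²; 2/0.343 = 5.8 L/m²
- 10 kg: √(10 × 76 / 3600) = 0.459 m²; 2/0.459 = 4.4 L/m²
- 20 kg: √(20 × 115 / 3600) = 0.799 m²; 2/0.799 = 2.5 L/m²
- 70 kg: √(70 × 170 / 3600) = 1.818 m²; 2/1.818 = 1.1 L/m²

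The protocol uses m² for activity and never for fluid. This step only checks that the pattern does not depend on choosing kg as the unit.

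**Step 3: what the protocol does with activity for the same children.** 50 × 0.343 = 17.1 mCi, which is 14% of 120 mCi; 50 × 0.459 = 23.0 mCi, which is 19%. Activity is cut to the child's size while the fluid volume stays at 100% of the adult figure. This says nothing about the correct fluid volume. It shows only that the protocol adjusts for size elsewhere and that footnote 10 does not.

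**Step 4: why the amino acid text is not used as a contrast.** Section 6.3 has a weight-based maximum rate, 8.3 mL/kg/hour, but adds "The total minimum volume which shall be infused is 1600 mL". In the stated 4 hours the rate delivers at most 8.3 × 4 = 33.2 mL/kg, so 1600 mL needs 1600/33.2 = 48.2 kg. Below about 48 kg the minimum is not reached in that time. That section therefore mixes scaled and fixed terms and is no clean example of scaling.

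**The case against.** **The relevant sheet may already cover children.** Footnote 10 says that patients will be instructed, and Appendix III lists Patient Home Going Instructions, a natural place for that instruction. The sheet was not in the text available. A reader might infer that the protocol package gives staff no paediatric fluid target at all. The documents do not support that; only the wording of footnote 10 can be judged. If the sheet has child volumes, footnote 10 conflicts with it and still needs the edit.

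**The large figures come from the extreme of the range.** They rest on assumed weights of 6.5 to 10 kg, and by 20 kg they have fallen to 75 to 100 mL/kg. Fluid need per kg also varies with age. A reader might take 200 to 308 mL/kg as a measured excess, or conclude that 2 L is wrong for everyone under 18. Neither follows: no benchmark of need is available here, no cut-off weight is shown, and an adult-sized adolescent may be well served by the printed volume. The objection stands on this point, which is why the proposed rule is a per-kg figure with an adult cap.

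**Practice lowers the risk.** Fluids may be IV or oral, so clinical judgment has room. The same investigators "have treated 18 children and young adults as well as 40 older adults", and section 1.5 reports no serious adverse events in the Phase I trial in children and young adults. This is reassuring, but the documents give neither the ages nor the volumes used, so it does not endorse 2 L/day for an infant.

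**The 1600 mL infusion minimum is also a fixed volume.** True, and editing footnote 10 does not touch it. It is a separate matter and does not make the footnote right.

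**Conclusion.** The point holds in a narrow form. Footnote 10, as printed, applies one adult-sized intake to every patient, including children from 6 months, and should not apply to small children. At assumed weights of 6.5 to 10 kg, 2 L/day is about 200 to 308 mL/kg, against 29 mL/kg at 70 kg. The direction does not depend on the exact weights, because any fixed volume weighs more heavily on a smaller body.

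The conclusion rests on the footnote text, the age criterion and the assumed weights. How many small children will enrol is not stated; that affects how often the rule would misfire, not whether it suits an eligible infant.

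Severity is minor to should-fix. A reader might infer that the trial's results or renal safety findings are compromised. Nothing in the documents shows that: no endpoint, sample size or decision rule depends on footnote 10, and no harm from it is reported.

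**What to change.** Reword footnote 10 so that:

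- 1.5 L on Day 1 and 2 L/day on Days 3 and 4 apply to adults (18 and over);
- subjects under 18 receive a stated mL/kg volume, with the figure chosen by the investigators and written into the footnote;
- that volume is calculated from the Day 1 weight and capped at the adult volume;
- the footnote and the Patient Home Going Instructions agree.

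The number itself should appear in the footnote. Leaving it to case-by-case discretion would replace an unsuitable rule with none.

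The weight is already collected, since calendar footnote 1 requires "Weight at baseline and Day 1 of each cycle". The cost is a short rewording and one check against the home-going sheet, with no added visits, procedures or subjects.

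One clerical correction can go in at the same time: the fluid diary row carries mark 11, which leads to the note on follow-up by a local physician. It should carry mark 10.

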6.1 Delivery of Therapeutic Infusion

⁹⁰Y-DOTA-tyr³-Octreotide and amino acid infusions will be administered on Day 2 of each treatment cycle. A large IV, either 20 gauge peripheral IV or a PICC line, will be inserted to provide free flow of the hyperosmolar amino acid solution, thus avoiding local inflammation with risk of blistering. Amino acid infusion will begin 30 min prior to infusion of ⁹⁰Y-DOTATOC and continue 3.5 hrs after infusion of radiotherapeutic drug. If rate of amino acid infusion is decreased due to nausea, the length of infusion

may be longer than 3.5 hrs. There will be rescue Sandostatin available (subcutaneous bolus of 200 µgm (200 µgm/mL)) in case of carcinoid crisis after ⁹⁰Y-DOTATOC infusion has been completed.

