6.2 Methods for Dosimetry Estimates

Renal dosimetry: Each subject will have renal ⁹⁰Y-DOTATOC time-of-flight (TOF) PET/CT images taken within approximately 48 hours (40-56 hours) after the administration of ⁹⁰Y-DOTATOC.

Bone Marrow dosimetry: Blood dosimetry will be performed as a surrogate of bone marrow dosimetry. Blood samples will be obtained prior to start of Amino Acid infusion, again within 1-4 hours after administration of ⁹⁰Y-DOTATOC and at 48 hrs (40-56 hrs).

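### The protocol requires no potassium value before an amino acid infusion, so high potassium at the start need not be identified until about three quarters of it has been given

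*Combined protocol and SAP*

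**What the plan says.** Footnote 3 of the calendar (section 7.0) defines the bloods at baseline and on Day 1 of each cycle: "blood tests include: CBC/diff, AST, ALT, creatinine, plus urinalysis at baseline only and T.Bili at baseline only". Potassium is not listed. For the Cycle 1 Day 1 tests, footnote 7 adds: "events only repeated prior to treatment 1 if they fall outside of the baseline windows noted in footnote 6". Bloods taken within the 10-day baseline window therefore need not be repeated.

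Inclusion item 10 (section 5.1) says "patients must have normal organ and marrow function as defined below". The definition covers neutrophils, platelets, bilirubin, transaminases, urinalysis and creatinine or GFR. Neither it nor the eligibility checklist in Appendix III has a potassium limit.

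On the treatment day, footnote 14 says "Electrolytes will be drawn during the last hour of amino acid infusion". Section 9.3 places the heart rate and potassium check 60 minutes before the end, with bicarbonate if potassium is above 6 meq/L and/or heart rate is below 60 bpm. Section 6.2 provides one earlier Day 2 sample, "Blood samples will be obtained prior to start of Amino Acid infusion", but for blood dosimetry only.

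Section 6.3 gives the infusion to all subjects over 4 hours, at up to 8.3 mL/kg/hr and no more than 450 mL/hr, and calls the volume off-label. It adds: "Initial infusion rate should be 300mL/hr or less; if tolerated for initial 30 min, rate may be increased to max rate" and "The total minimum volume which shall be infused is 1600 mL".

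**The concern.** Section 9.3 recognises potassium disturbance as an effect of this infusion and sets up a check for it. That check can detect and treat a high value late in the infusion. It cannot stop a subject whose potassium is already high from starting. No required test does that.

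The clearest reason for concern comes from section 10.1. Subjects whose nuclear GFR falls by 30% or more are put on an ACE inhibitor and may receive the next cycle at half the radioactive dose. The amino acid infusion is not reduced for them and no potassium check is added. That reduced GFR and ACE inhibition tend to raise potassium is general clinical knowledge, not something the documents state. At stake is the safety of individual subjects, not the validity of any analysis.

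**Working it through.** **Is potassium required anywhere before an infusion?**

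- Baseline and Day 1 bloods (footnote 3): not listed.
- Inclusion item 10 and the checklist: no limit.
- Day 2 sample before the infusion (6.2): dosimetry only.
- Electrolytes (footnote 14) and potassium (9.3): last hour of the infusion.
- Cycles 2 and 3: a value exists from the previous cycle, but it was drawn during that infusion, 6 to 8 weeks earlier.

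No provision requires it.

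**How much has been infused at the check?** Section 6.1 gives 0.5 h before plus 3.5 h after the radioactive drug, or 4.0 h, which reproduces the 4 hours in section 6.3. The check falls at 4 − 1 = 3 h.

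- *Maximum adult rate* (300 mL/hr for 0.5 h, then 450 mL/hr). By 3 h: 0.5 × 300 + 2.5 × 450 = 1,275 mL. By 4 h: 0.5 × 300 + 3.5 × 450 = 1,725 mL. Share: 1,275/1,725 = 73.9%. Weight needed for 450 mL/hr: 450/8.3 = 54.2 kg.
- *Minimum volume in 4 h.* Rate after the first half hour: (1,600 − 150)/3.5 = 414.3 mL/hr. By 3 h: 150 + 2.5 × 414.3 = 1,186 mL. Share: 1,186/1,600 = 74.1%. Weight needed: 414.3/8.3 = 49.9 kg.
- *Slowed infusion.* Section 6.1 allows this: "If rate of amino acid infusion is decreased due to nausea, the length of infusion" may exceed 3.5 hours. At 300 mL/hr throughout, 1,600 mL takes 1,600/300 = 5.33 h. The check is at 4.33 h, with 1,300 mL in. Share: 1,300/1,600 = 81%.
- *Sensitivity.* If the radioactive infusion itself adds 15 to 30 minutes (an assumption), the share by time is 3.25/4.25 = 76% to 3.5/4.5 = 78%.

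Footnote 14 taken alone allows a draw at any point in the last hour, and laboratory turnaround adds to the delay.

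**Smaller subjects.** Below about 50 kg the weight cap and the 1,600 mL minimum cannot both be met in 4 hours. At 20 kg the cap is 8.3 × 20 = 166 mL/hr, or 664 mL in 4 hours. The text does not say which rule gives way, so no share is claimed for this group.

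**What rate do the documents give?** Only the one exception in more than 400 infusions in section 9.3. Applied to three infusions per subject, 1 in 400 gives 138/400 = 0.35 events for 46 subjects (section 12.1) or 192/400 = 0.48 for 64 (section 8.2). This concerns disturbance with the infusion, in adults. It is not a rate of high potassium beforehand.

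**The case against.** The strongest reply is that the late check is deliberate. Section 9.3 describes a disturbance seen with the infusion, so measuring when most of the volume is in makes sense. The changes seen were unimportant and resolved, apart from one exception in more than 400 infusions. The documents report no case of high potassium before infusion. This stands, and it is why the point is minor. But a pre-infusion value answers a different question, which the late check cannot.

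There are also indirect safeguards: creatinine or GFR entry limits, Day 1 creatinine, nuclear GFR where indicated, the medication list, pulse on Days 1 and 2, 18 hours of fluids beforehand, exclusion of uncontrolled illness including arrhythmia, and the investigator's freedom to stop treatment. After a renal dose-limiting toxicity, section 10.1 requires recovery before re-treatment. Section 13.3 reports no irreversible renal toxicity in 18 younger and 40 older patients. These narrow the group at risk, but none of them measures potassium. The recovery rule does not reach subjects with a GFR fall between 30% and 50%, who may be re-treated.

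A reader might infer that subjects with high potassium will in practice go unnoticed until late. The documents do not support that. They show what is required, not what is done: footnote 3 is worded as a list of what the tests include, the schema says only labs, and section 6.3 refers further dosing questions to the manufacturer's instructions. Sites may already check potassium.

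**Conclusion.** The gap is real and of low severity. Following the protocol as written, a subject with high potassium may start an infusion of off-label volume and need not be identified until about 74% of it is in at adult rates, or 81% if it is held at 300 mL/hr. These figures assume the check is made 60 minutes before the end, as section 9.3 says, and a weight of at least about 54 kg for the maximum-rate case or 50 kg for the minimum-volume case.

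The percentages measure volume, not harm. A reader might take them to imply an appreciable number of injuries. The documents give no rate of high potassium before infusion, and their one related figure points to a low absolute risk, so no expected number of cases is claimed. The efficacy analysis and the stopping rules in sections 8.2 and 12.2 are unaffected.

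**What to change.** Add potassium to the Day 1 bloods of each cycle in footnote 3, and state that footnote 7 does not waive it at Cycle 1 Day 1. State in section 9.3 that a pre-infusion value above 6 meq/L, or a lower limit chosen by the investigators, is repeated or treated before the infusion starts. The investigators should consider a lower limit: 6 meq/L is the late-infusion treatment threshold, so a subject just below it would proceed unchanged. Keep the late check.

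Day 1 is better than the Day 2 dosimetry sample. By Day 2 the product may already be made, and whether a dosimetry sample exists in Cycle 3 is unclear: the calendar marks one, while section 10.1 places dosimetry after treatments 1 and 2.

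The cost is about three assays per subject (46 × 3 = 138, or 64 × 3 = 192), on planned draws. A small extra draw is needed at Cycle 1 Day 1 where footnote 7 has removed the other bloods. Occasionally a treatment will be delayed or held. A batch could then be lost, since section 13.1.1 says preparations are usually for a single patient and expire in 48 hours. No visit is added, and sample size and analysis do not change.
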